9.4.3 Potential Benefits of Trial Participation

Carrying out this research in the pediatric setting will likely increase the provision of tobacco control services for parents who smoke. Increased provision of services has been proven to increase the chances of changing smoking behaviors. Parents who successfully quit or reduce their tobacco consumption may live longer with a better quality of life, reduce the tobacco smoke exposure of their spouses, children, and others, and have increased financial resources. Mothers who quit successfully may be non-smokers for subsequent pregnancies, leading to better outcomes for their unborn children. The children of parents who quit smoking are less likely to grow up to be smokers themselves. However, these benefits cannot be guaranteed to all parents and families who participate in the research.

In addition to the potential benefits to participants, the benefits of this study will include improvement of science and clinical practice. The results will also help to develop and implement fully integrated, cost-effective, disseminable, and sustainable strategies to optimize parental smoking cessation outcomes in pediatric settings on a national scale. The minimal risks of participation are reasonable in relation to the potential benefits of these interventions. It is also possible that the information obtained from this project will be used to develop clinician guidelines and education, which could directly benefit the study subjects in the future.

9.4.4 Risk-Benefit Assessment

Risks to participants will be minimal and include discomfort in discussing personal tobacco use with a stranger, and the receipt of tobacco-related services from their child's clinician. Study participants will lose approximately ~ 15 minutes of time that they could have used for other activities. In addition, subjects will be asked to participate in the longitudinal cohort survey 12 months after the index visit, which will take approximately 15 minutes at the practice exit or remotely and if eligible, giving a salivary sample and doing a CO breath test. The same risks apply.

Carrying out this research in the pediatric setting will likely increase the provision of tobacco control services for parents who smoke. Increased provision of services has been proven to increase the chances of changing smoking behaviors. Parents who successfully quit or reduce their tobacco consumption may live longer with a better quality of life, reduce

the tobacco smoke exposure of their spouses, children, and others, and have increased financial resources. Mothers who quit successfully may be non-smokers for subsequent pregnancies, leading to better outcomes for their unborn children. The children of parents who quit smoking are less likely to grow up to be smokers themselves. However, these benefits cannot be guaranteed to all parents and families who participate in the research.

9.5 Recruitment Strategy

As part of the clinical workflow, all parents in control and intervention practices will be asked about their individual smoking status on the iEHR pre-visit screening questionnaire (Appendix 5 for intervention practices and Appendix 5A for control practices).

The study team/CHOP Clinical Reporting Unit (CRU) and/or Research Enhancement Core (REC) will generate rosters of potentially eligible parents for the upcoming visit. Rosters will include all upcoming visits at study practices of parents who answered, “yes” to either of the screening questions: *“Have you smoked a cigarette, even a puff, in the past 7 days?”* and *“Have you smoked any other tobacco product (cigars like black and mild, hookah), even a puff, in the past 7 days?”* on the iEHR pre-visit screening questionnaire. The study team will approach these potentially eligible parents to offer enrollment in the study.

Additionally, at participating CHOP primary care sites, study team will also review the medical records to identify parents who self-reported as smokers (answered “yes” to either of the screening questions: *“Have you smoked a cigarette, even a puff, in the past 7 days?”* and *“Have you smoked any other tobacco product (cigars like black and mild, hookah), even a puff, in the past 7 days?”* on the iEHR pre-visit screening questionnaire. (Appendix 5 for intervention practices and Appendix 5A for control practices) to approach them and offer enrollment in the study longitudinal cohort.

Potentially eligible families who are missed in the CHOP primary care sites or are not able to complete enrollment survey in the office will also be reached via recruitment emails (Appendix 12 (for intervention) and 13(control)), text messages and calls facilitated by the study team and/or CHOP Research Enhancement Core (REC).

We will deploy several strategies to maximize recruitment. Parents will be recruited in one of these ways: (1) In-office enrollment; (2) Hybrid enrollment: from in-office to remote; (3) Remote enrollment. The detailed description of each approach and overall recruitment strategy is described in detail under section 4.1. Screening & Enrollment.

Using these strategies, we will continue to enroll parents until approximately 100 parents who use combusted tobacco have been enrolled in the longitudinal cohort in that practice or approximately 400 parents who use combusted tobacco are enrolled in each arm. If some

practices accrue subjects at a rate which makes it unlikely that these practices can achieve the recruitment goal of approximately 100 subjects, then we will estimate the likely shortfall, and increase the recruitment goals in faster-accruing practices in order to attempt to preserve statistical power. If enrollment is slower than projected in some practices, we will add new practices that are similar to each other based on practice size and Medicaid rate in each arm to reach the goal of 400 parents in each arm.

A notice may be posted at the practice entrance/registration window/waiting room of participating practices, informing parents accompanying their children to office visits that the practice is participating in the research study (posting details may be modified based on practice layout and preferences). Recruitment procedures will be identical across both arms.

9.6 Informed Consent/Accent and HIPAA Authorization

For in-person parent consent, the trained research assistants at the practices will approach eligible participants (screened through the review of medical records) and ask whether they want to participate in the study. They will be given the appropriate consent documents at this time to read prior to completing any parent enrollment surveys. REDCap will be the primary method of obtaining consent from participants. Research Assistants will provide tablets with the REDCap eConsent, and participants will be provided with a copy of the signed document via email. The eConsent forms were reviewed and authorized for use by the CHOP REDCap team. In case of a tablet failure/unavailability, paper consent forms will be used. For paper consent, trained research assistants will document consent by obtaining the participant's signature on the previously approved IRB consent document.

For remote parent consent, consent will be obtained electronically utilizing the REDCap interface, accessed by a link emailed or texted to the participant. When consent is obtained electronically, participants will be able to read, digitally sign their name and receive an emailed copy of the informed consent/HIPAA authorization form. The research presents minimal risk to participants and involves no procedures for which written consent is normally required outside of the research context. When parent outreach is performed via a phone call, a study team member will be able to answer any questions about consent in real time. Study team's phone number and e-mail address will be included in all e-mail and text communication with parents.

The parent consent form (Appendix 3 and 3b (paper) and 3E and 3bE (electronic) will describe the risks, benefits, and rights of participation, as well as an assurance of confidentiality, including the procurement of a federal Certificate of Confidentiality. The study staff will review the documents with the family and answer any questions and give them time to decide if they want to enroll in the study. For electronic consent, the parent will be asked to electronically sign the REDCap consent form if they elect to participate and will be provided with a copy of the signed consent via email. In case of paper consent, the parent will be asked to sign and return

the appropriate consent forms if they elect to participate, retaining a copy of each form for their own records.

In intervention practices, in-depth qualitative interviews will be conducted with practice clinicians and staff 6-weeks following implementation and at 12, and 24 months.

The clinician and staff consent form (Appendix 8) will describe the purpose of the interviews, risks, benefits and rights of participation, as well as an assurance of confidentiality, including the procurement of a federal Certificate of Confidentiality. The completed paper consent forms will be kept in a locked location at CHOP and kept in a locked location at CHOP for 10 years and then destroyed. Electronic clinician consent forms will be stored securely on the REDCap server.

The consent form will be a combined consent-authorization document.

9.6.1 Waiver of Consent

n/a

9.6.2 Waiver of HIPAA Authorization

For parent subject, we incorporated a HIPPA Authorization form in the Consent Form using appropriate consent templates (Parent Consent Forms Appendix 3, 3b, 3bE, 3E).

For clinician and staff participants of the qualitative interviews we would like to request a waiver of HIPPA Authorization as we will not be collecting any protected health information for these subjects.

We would like to request a waiver of HIPAA authorization for recruitment of parents, as the study staff will need review patient medical records to identify eligible subjects (as part of recruitment). This way we can target our recruitment only to those parents who identify as smokers.

9.7 Payment to Subjects/Families

9.7.1 Payments to parent for time and inconvenience (i.e., compensation)

- \$20 gift card will be provided to parents upon participating in the enrollment survey at baseline
- \$40 gift card will be provided to parents upon participating in the follow-up survey respectively.
- \$50 gift card will be provided to parents who provide a salivary sample to confirm quit status.

- \$50 gift card will be provided to parents who do the CO breath test to confirm quit status.

Participants can get the gift card via e-mail, text, or in-person.

9.7.1.1 *Token of Appreciation*

During the navigator sessions (protocol section 4.2.2), the navigator can offer families a small item, such as a stress ball, a motivational journal, a key chain, or a coloring book, something that parents can use to distract themselves from smoking or remind them why they want to quit in the first place. CHOP community health navigators already incorporate this strategy when working with families.

9.7.2 Payments to practices for time, effort and inconvenience (i.e., compensation)

N/A

9.7.3 Payments to clinicians and staff for time, effort and inconvenience (i.e., compensation)

A \$50 gift card will be given to the clinicians and staff to recognize their time and effort for participating in the qualitative interviews (\$50 per interview).

10 PUBLICATION

There will be sub-committee, “**Publications, presentations, and dissemination**” which will include both MGH and CHOP members. No individually identifiable PHI will be published. Both MGH and CHOP team members will have access to the complete trial data and will work together to write papers. Both team members will discuss the papers related items and analysis plans in this sub-committee meeting.

APPENDIX

- Appendix 1: Recruitment e-mail letter to CHOP practices
- Appendix 2: Qualitative interview information Sheet
- Appendix 3, 3b, 3E and 3bE: Intervention and Control practices parent consent
- Appendix 4: Parent enrollment survey
- Appendix 5: CEASE pre-visit screening questionnaire (Intervention)
- Appendix 5A: CEASE pre-visit screening questionnaire (Control)
- Appendix 6: 12-month follow-up survey
- Appendix 7: Qualitative interview guides
- Appendix 8: Clinician consent form
- Appendix 9: Cost-effectiveness direct observation log
- Appendix 10: Eligibility Form
- Appendix 11: Navigator Form
- Appendix 12: eCEASE INTERVENTION Recruitment Email Template
- Appendix 13: eCEASE CONTROL Recruitment Email Template

Title: **Electronic Pediatric Office Systems to Support Treatment for Parental Tobacco Use**

Short Title eCEASE

Drug or Device Name(s): N/A

NCT Number: NCT04974736

Sponsor: NIH

eIRB Number: IRB 20-018146

Version Date: 11/10/ 2020

Statistical Analysis plan.

Primary outcome: Parental 7-day quit rates, as assessed by validated surveys and biochemically- confirmed at 12-months, compared between iEHR+Navigator and usual care control arms. The study is powered for this outcome.

The primary outcome will compare the parental combusted tobacco cessation, biochemically confirmed between the intervention arm (iEHR + Navigator) vs. usual care control. For cotinine confirmed quitting, only self-reported non-smokers who have cotinine values <10 ng/ml, a consensus cutoff level, will be considered quit. Parents on NRT, or e-cigarettes, or who fail the cotinine test will be asked to have their carbon monoxide (CO) levels tested, to confirm self-reported smoking cessation. For CO confirmed quitting, expired-air CO cutoff level of < 5ppm will be considered quit. E-cigarette use will be noted and analyzed separately as the literature emerges.

In our intention-to-treat analysis, all participants lost to follow-up will be considered smokers. We will also use multiple imputation techniques, as appropriate to impute missing data. We will use generalized linear mixed-effects models (Gaussian, logistic, or Poisson, as appropriate) to compare the primary outcome between arms. To the extent allowed by the sample, we will build a logistic regression model that includes potential confounding factors, particularly those that are unbalanced between iEHR+Navigator vs usual care control groups to compare the parental 7-day quit rates. We will attempt to identify predictors of parental quitting to determine whether any of these factors modify intervention effect. To determine whether the intervention effect differs among subgroups, we will test the interaction between intervention group and these predictors. Specifically, to the extent allowed by our sample size, exploratory analyses will compare quit rates in subgroups of smokers characterized by cigarettes per day, e-cigarette use, number of smokers in the home, demographic variables (parent sex, age, race, education, child age) and treatment use. We will conduct a difference in difference analyses from baseline to follow up to evaluate the effect of the intervention on changes in smoking related factors like mean cigarettes per day and daily smoking rates.

Secondary outcomes

1. Rates of smokefree homes and cars, use of NRT and duration of use, and quitline enrollment, as assessed by validated surveys of parents, will be compared between iEHR+Navigator and usual care control arms. Change in parental smoking inside homes and cars, use of NRT, and receiving services from cessation programs will be based on the baseline and 12-months enrollment visit, comparing change from baseline to 12 months between intervention groups and usual care control practices. We will follow a similar analysis strategy to that stated above in primary outcome analysis.

2. Establish the incremental cost per quit of intervention. The healthcare system's perspective is central to establishing the interventions' disseminability and sustainability. As a secondary analysis, we will consider costs from a societal perspective to pave the way for future cost-utility analyses. We will calculate the incremental cost per quit of the iEHR+Navigator intervention relative to usual care, as we have done in prior studies: $(\text{Total cost at 12 months}_{\text{arm[i]}} - \text{Total costs}_{\text{arm[j]}}) / (\text{Total biochemically confirmed quits at 12 months}_{\text{arm[i]}} - \text{Total biochemically confirmed quits at 12 months}_{\text{arm[j]}})$. Development costs for iEHR will not be included in primary analyses as the iEHR will be fully developed and ready for dissemination by the time the intervention begins. Direct costs include iEHR set-up, customizing, implementing, and sustaining the systems changes that support service delivery and cessation, electronic tablets, and related clinician work. Direct costs further include: the CEASE intervention staff time to support the practice leader and the time clinicians and office staff take to learn and use the online module. Time use will be tracked by administrative records, direct observation by the RA, and surveys. For the iEHR+Navigator arm, we will create a log to note the types of CHN outreach efforts, time spent, and the type of services delivered to smoking parents. Personnel costs will reflect national average wages for each personnel type. We will use Monte Carlo simulation methods to develop confidence bounds on our cost-per-quit estimates. Following standard methods of economic evaluation in prior studies, we will also perform parameter-specific sensitivity analyses in which individual parameters are varied singly and in combination, through plausible ranges to assess the relative impact different elements of the program have on overall cost-effectiveness.

3. Assess the implementation and sustainability of the intervention in the iEHR + Navigator arm **NRT prescription, quitline referral, and smokefree homes and cars will be compared between iEHR+Navigator vs. usual care control, as assessed by parental surveys at 12-months, and by EHR documentation data at, before, and immediately following implementation at 6,12, 18, 24, 30, and 36 months (documentation of screening and services delivery fidelity, coding, and billing).** We will follow a similar analysis strategy to that stated above in primary outcome analysis. We will compare cessation assistance delivery at 6 months intervals for 3 years using EHR documentation data. We will analyze qualitative interview data from the combined RE-AIM/CFIR interviews conducted at before and following implementation, and at 12, and 24 months. The interview data will be coded and thematically analyzed in order to gain clarity on implementation processes and intervention sustainability. The interview data will inform future implementation and sustainability efforts.

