3 INVESTIGATIONAL PLAN

3.1 General Schema of Study Design

This is a stratified cluster randomized controlled trial of minimum 8 child primary care practices with minimum 4 practices each randomized to iEHR + Navigator or usual care control arms:

¹Practices will be randomized to 2 arms, with 4 sites in each arm and ~400 parent subjects per arm (~100 per site). Approximately 800 parent subjects across 8 sites (~100 per site) will be enrolled. Enrolled parents will be followed up at approximately 12 months (could be sooner or later depending on the visit schedule/parent availability).

²Parent screening and enrollment procedures may be modified to kiosk/telephone/remote screening and enrollment due to procedures that may be in place at CHOP to protect people from COVID-19 risks.

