6.4 Sample Size and Power

Sample size calculations are based on having at least 8 practices with a minimum of 5 clinicians per practice. Clinically important and conservative estimates of validated 12-month quit rates based on prior studies are 13.8% in the iEHR + Navigator group and 7% in the usual care control group. These estimates are based on the worst-case scenario from prior studies where all enrolled parents lost to follow-up were assumed to be smokers at 12-month follow-up. The effective sample size needed for the primary outcome accounts for clustering at the clinician and practice level (4 practices per arm x 5 clinicians per practice) with intra-class correlation of .014 calculated from our previous research. By enrolling approximately 100 parents in each practice (400 per arm), we will have 80% power for the primary outcome (iEHR + Navigator vs. usual care control). Effect sizes for outcomes other

than cessation will likely be much greater; the study will have adequate power to detect these differences, shown in our prior studies.

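### The SAP plans two between-arm tests of the primary quit rate, does not say which decides, and does not state that the second keeps a practice effect

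*SAP*

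**What the plan says.** The SAP's primary outcome text gives two consecutive comparisons of arms on one endpoint.

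- First: "We will use generalized linear mixed-effects models (Gaussian, logistic, or Poisson, as appropriate) to compare the primary outcome between arms". The random effects are not named, and no reference distribution for the test is given.
- Second: "To the extent allowed by the sample, we will build a logistic regression model that includes potential confounding factors", and among those factors "particularly those that are unbalanced between iEHR+Navigator vs usual care control groups to compare the parental 7-day quit rates". The SAP names the biochemically confirmed 7-day quit rate as the primary outcome, so this is the same endpoint.

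Neither is called primary, supportive or sensitivity. Protocol sections 6.1 to 6.4 name no model, so they do not settle it. Other analyses do have a status: the SAP calls its subgroup comparisons exploratory, and the statistical plan in the protocol synopsis calls multiple imputation a sensitivity analysis.

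On design, protocol section 3.1 states: "This is a stratified cluster randomized controlled trial of minimum 8 child primary care practices". Section 9.1.1 randomises practices within matched pairs. Section 6.4 says the sample size "accounts for clustering at the clinician and practice level (4 practices per arm x 5 clinicians per practice"), using an "intra-class correlation of .014 calculated from our previous research".

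**The concern.** Two things are left open.

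1. **Which test decides.** If the two disagree, the plan does not say which one carries the conclusion on the only outcome for which the study is powered. The second is also a family of models rather than one, because its covariates depend on observed imbalance and on what the sample will bear.
2. **Whether the second test respects the randomised unit.** The SAP specifies mixed effects in one sentence and does not repeat it in the next. An analyst following the text could fit an ordinary logistic regression to about 800 parents from about 8 practices. Its standard error would be too small whenever quit rates vary between practices or clinicians.

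The SAP applies a similar strategy to its survey and implementation outcomes, so the ambiguity carries over to them.

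**Working it through.** **Inputs.** From protocol section 6.4: quit rates of "13.8% in the iEHR + Navigator group and 7% in the usual care control group"; ICC .014; 400 parents per arm in 4 practices of 100, each with 5 clinicians, so 20 parents per clinician. Neither document states alpha or sidedness; two-sided 5% is assumed.

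**Step 1. Reproduce the protocol's power.** The claim is: "By enrolling approximately 100 parents in each practice (400 per arm), we will have 80% power for the primary outcome". Take DEFF = 1 + (m − 1) × ICC and effective n = 400 / DEFF in the two-proportion formula.

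| Clusters | m | DEFF | Effective n per arm | Power |
|---|---|---|---|---|
| Clinicians | 20 | 1 + 19 × .014 = 1.266 | 316 | 80.1% |
| Practices | 100 | 1 + 99 × .014 = 2.386 | 168 | 53.2% |

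The stated 80% reproduces with clinician clusters only. A one-sided test there would give 87.7%, which supports the two-sided assumption.

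**Step 2. False-positive rate of a logistic model with no cluster term.** The true variance is DEFF times the assumed one, so the rate is 2 × [1 − Φ(1.96 / √DEFF)].

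- Clinician clustering: 1.96 / √1.266 = 1.742, giving 8.2%. Beta-binomial simulation at a 7% quit rate gave 7.8%.
- Practice clustering: 1.96 / √2.386 = 1.269, giving 20.5%. Simulation gave 19.9%.
- Practice clustering with more practices and about 400 parents per arm, simulated: 17% (5 per arm), 15% (6 per arm), 13% (8 per arm).

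**Step 3. Is it the second test or the missing cluster term?** In 1,500 simulated null trials with practice-level ICC .014, the unclustered model was significant in 19.9%. Either it or a random-intercept logistic model was significant in 20.0%. The missing cluster term accounts for nearly all of the inflation.

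**Step 4. The second model keeps the practice effect.** Here an unadjusted and an adjusted practice-level comparison were simulated, each with t on 6 df. With covariates assumed to explain 5%, 10% or 20% of within-practice variance, at least one test was significant in 5.8%, 6.3% and 6.8% of null trials. Two fully independent tests would give 1 − .95² = 9.75%.

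**Step 5. Is naming the mixed model enough?** With 4 practices per arm and practice-level ICC .014, a random-intercept logistic model with a Wald z test gave 10.1% false positives in one simulation and 12.6% in another. With t on 6 df, the first simulation gave 4.5%.

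**The case against.** The strongest reply is that the second model is simply the covariate-adjusted version of the first. The preceding sentence lists logistic as one family of mixed-effects model, and protocol section 6.4 shows that the team treats clustering as part of the primary comparison. This is a fair reading. A reader might infer that the second model definitely lacks a practice effect, but the SAP is silent, so the 8% and 20% figures are conditional on the literal wording.

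A reader might also infer that a win on either test counts. The documents contain no such rule. The mixed model is the one assigned to the primary comparison, while the adjusted model is conditional on the sample and leads into predictors and exploratory subgroups. The order suggests a hierarchy, but it is not written down. The statisticians also stay blinded to which label is the intervention until the analyses are done (protocol sections 9.1.1 and 9.1.2). That limits picking the favourable result, but it does not hide which model gives a small p-value.

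Finally, the 20% end needs practice-level clustering and exactly 4 practices per arm. Because the protocol's power reproduces with clinician clusters, its own calculation points to the 8% end. Eight practices is a minimum.

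What remains is that no deciding test is named, the practice effect in the second model is unstated, and its covariates are data-driven.

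**Conclusion.** The point holds as a gap in the specification with a conditional consequence. The SAP has two unranked comparisons of its one powered outcome, and its wording permits the second to ignore the randomised unit.

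Under a two-sided 5% test, 4 practices of 100 per arm and ICC .014, that literal second model has a false-positive rate of about 8% (clinician clustering) to 20% (practice clustering), or about 13-17% with 5 to 8 practices per arm. If both analyses keep a practice effect and a small-sample reference, the chance of at least one false positive is only about 6-7%.

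The documents do not support quoting 8-20% as the trial's overall error rate. Nor do they support a figure for how often the two tests would disagree, because that depends on a random effect and a reference distribution that the SAP does not specify.

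**What to change.** In the SAP's primary outcome analysis:

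1. Name one deciding test: the mixed-effects logistic model with a practice effect, on the data set that counts parents lost to follow-up as smokers. Specify a small-sample reference, such as t with between-practice degrees of freedom (8 − 2 = 6 for 8 practices), instead of Wald z.
2. Replace the separate logistic regression with a refit of that same model, with the same practice effect and small-sample reference. Add covariates prespecified from the baseline data rather than chosen by observed imbalance.
3. Label that refit and the multiple-imputation result as sensitivity analyses that cannot change the primary conclusion. The protocol synopsis already does this for multiple imputation.

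This takes a few sentences and no extra data. The cost is wider intervals and lower nominal power. Using the design rates and a non-central t with 6 df, with effect 0.068 over its unpooled standard error, power is about 65% with clinician clustering (0.068 / 0.0241) and about 41% with practice clustering (0.068 / 0.0331). The normal-approximation values were 80.1% and 53.2%.
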